12.3 Sample Size and Accrual Rate

The 2-stage Simon optimal design, as described above, will require up to 24 response evaluable patients. Accounting for up to 10% inevaluable patients that need to be replaced, the maximum accrual for the study will be 27 patients. Combining all participating sites, we project that the study accrual can be completed within 2 years, with an estimated accrual rate of approximately 1 patient per month.

12.4 Interim Analyses/Stopping Rules

12.4.1 Interim Efficacy Monitoring

The study will perform an interim analysis of CR rate per the Simon's 2-stage rule as described above in Section 12.1.

12.4.2 Toxicity Monitoring

We will monitor the rate of the following adverse events that are **at least possibly** related to protocol treatment at any time during study treatment:

- Grade ≥ 3 diarrhea which does not resolve within 3 days with best supportive care
- Febrile neutropenia
- Grade ≥ 2 pneumonitis
- Grade ≥ 4 elevations of AST, ALT or Grade ≥ 3 elevation of bilirubin
- Grade ≥ 4 infection
- New onset grade 4 atrial fibrillation in patients without a history of atrial fibrillation
- Major hemorrhage defined as serious or Grade 3 or higher bleeding or any central nervous system bleeding.
- Severe (grade 4) cutaneous reaction

This monitoring will include all patients who received at least 1 dose of the protocol treatment. The expected rate of patients having any of these toxicities should be <33%. The first monitoring will occur when the 6th patient completes the first induction cycle, and it will include all available cycles from the first 6 patients. If more than 1 patient experience any of the toxicities above at the first monitoring, accrual will be halted; study data will be reviewed by the study committee and the City of Hope Data and Safety Monitoring Committee (DSMC). Study amendment may be proposed if necessary. Accrual will not be resumed until approved by DSMC. If 0 or 1 patient has these toxicities at the first monitoring, accrual will continue as planned and the result of this first monitoring will be submitted to DSMC at the next PMT report. Subsequent monitoring will be performed every 6 months as part of each PMT report. If at such review 33% or more of the patients experience these toxicities, the study accrual will be temporarily halted; a full review of these events and other toxicities will be performed by the study team and DSMC. Patient accrual will not resume until approved by the DSMC to do so. In addition, COH DSMC will review all toxicities every 6 months and may make their independent assessment and recommendations.

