5.7 Follow-Up

Following completion of protocol therapy, participants will enter follow-up.

Follow-up is comprised of:

- **Safety Follow-up**- 30 days post-last dose of protocol therapy.
 - **Note** the period for safety follow-up will be extended until stabilization or resolution for all reportable AEs (per the agreement of the Study PI) and accompanying follow-up safety report.
- **Response Follow-up**- for those who have yet to have disease progression and have not initiated a new anti-lymphoma therapy.

- **Survival Follow-up**- for all participants who have progressed OR completed Active Response Follow-Up OR initiated a new anti-lymphoma therapy. It will entail (a) Disease status (for those who have yet to progress) (b) Vital status (all participants).

Assessment time points and windows are detailed in [Section 10](#).

Note: if a participant continues therapy beyond 25 cycles with acalabrutinib for a total of 6 years of protocol therapy, the participant will only proceed with the safety follow-up visit; there will be no response/survival follow-up.

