14.4 Routine AE Collection and Reporting Guidelines

AEs will be collected from the signing of informed consent until ending study participation. Routine AE reporting will occur via data entry into the study eCRF. AEs will be monitored by the Protocol Management Team (PMT). AEs reported through expedited processes (e.g., reported to the IRB, DSMC, FDA, etc.) must also be reported in routine study data submissions.

AEs recorded in the eCRF include:

- For each cycle and safety follow-up period, all grade 3 and higher AE for each type **AND** the highest grade of AE for each type (if grade 1 or 2)
- All SAEs

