14.5 Expedited Reporting

Table 14.5 indicates what events must be reported expeditiously.

Table 14.5 Criteria for Expedited Reporting

Time point	What to report
From signing of the consent to study completion	
• All UPs
From signing of the consent to treatment initiation	
• All SAEs
For the time period beginning at treatment through 30 days following cessation of treatment	
• All SAEs* regardless of relationship to protocol therapy• All UPs and AEs that meet the definition of a UP• Ventricular arrhythmias (Section 14.2.1)• Abnormal liver function tests (Section 14.2.3)• Overdose of acalabrutinib, ublituximab or umbralisib (Section 14.3.1)• Pregnancies and lactation
From Day 1 of protocol therapy up to 2 days post last dose of acalabrutinib and 30 days post last dose of ublituximab or umbralisib	
• Pregnancies and lactation
Post Safety Follow-Up to removal from study	
• All SAEs* that are considered probably or definitely related to acalabrutinib, umbralisib or ublituximab

NOTE: All events reported expeditiously require follow-up reporting until the event is resolved, stabilized, or determined to be irreversible by the investigator.

The DCC should be consulted prior to ending the follow-up of events that have stabilized.

* Refer to [Section 14.7](#) for guidelines on reporting secondary malignancies to the industry partners.

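### The toxicity halt rule in 12.4.2 stops counting when study treatment ends, so a first related event in the 30-day Safety Follow-up is recorded but does not count towards a halt

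*Combined protocol and SAP*

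**What the plan says.** Section 12.4.2 lists eight kinds of adverse event and monitors those at least possibly "related to protocol treatment at any time during study treatment". On the denominator it says: "This monitoring will include all patients who received at least 1 dose of the protocol treatment".

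There are two triggers. The first look comes when the sixth patient completes the first induction cycle, and "it will include all available cycles from the first 6 patients". The rule there is: "If more than 1 patient experience any of the toxicities above at the first monitoring, accrual will be halted". Later looks come every six months with the PMT report: "If at such review 33% or more of the patients experience these toxicities, the study accrual will be temporarily halted". The same section has the DSMC review all toxicities every six months and allows it to make its own recommendations.

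Other sections carry safety past the last dose. Section 5.7 sets a Safety Follow-up at "30 days post-last dose of protocol therapy", as part of the follow-up entered once protocol therapy is complete. Section 14.4 puts into the eCRF "For each cycle and safety follow-up period, all grade 3 and higher AE", together with the highest grade of lower-grade events. Table 14.5 requires all SAEs, whatever their attribution, "For the time period beginning at treatment through 30 days following cessation of treatment".

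**The concern.** Numerator and denominator do not cover the same time. A patient who ends all three agents remains in the denominator at every later review, yet a first listed event after that point cannot enter the numerator. Measured against the safety period the protocol uses elsewhere, the counted proportion can be too low but never too high.

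The patients affected are those who have come off treatment, and Section 5.6 names intolerable toxicity as one reason for coming off. Examples are a related grade 4 infection or grade 2 pneumonitis first appearing on day 15 after all agents have been permanently ended. Either event would be in the database, and the rule as worded would not use it.

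The margin at the first look is one patient: 2 of 6 halts accrual and 1 of 6 does not.

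**Working it through.** **Does the wording reach past the last dose?** Study treatment is not formally defined. Three places bear on it.

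- Section 5.7 places Safety Follow-up after completion of protocol therapy, so it is a separate period.
- Section 14.4 names cycles and the safety follow-up period separately. The first look in 12.4.2 is stated in cycles only.
- Section 5.9.2, written for prohibited medications, ends protocol therapy at the later of the last day of study agent and the decision to end it.

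None of these extends study treatment through the 30 days. The most generous, 5.9.2, moves the end to the date of the decision to stop.

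**Who is affected?** Only a patient off all agents whose first listed event comes afterwards. Sections 5.6 and 7.1 let a patient stop one agent and continue the others, and 7.1 allows delays of up to 8 weeks. Such patients are still on study treatment and their events count. The full 25 cycles last 25 × 28 = 700 days, about 23 months, against 2 years of accrual (Section 12.3). While accrual is open, the gap therefore concerns mainly patients who stop early.

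**Are the two thresholds consistent?** Yes: 2/6 = 33.3%, in line with the later 33% rule. The smallest count reaching 33% is 4 of 12 (0.33 × 12 = 3.96), 6 of 18 (5.94) and 8 of 24 (7.92). Section 12.4.2 states no operating characteristics for this rule, so there is no plan figure to reproduce.

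**What could the gap do to the halt probability?** Let p be the true proportion of patients with a listed event through 30 days after the last dose, and f the share of those patients whose first event falls after treatment ends. The rule then sees q = p(1 − f), and the single-look chance of reaching halt count k among n patients is P(X ≥ k), with X binomial(n, q). The values of f are assumptions, because the documents give none.

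For p = 0.33, q is 0.33, 0.3135, 0.297 and 0.264 at f = 0, 5%, 10% and 20%. Worked at n = 6, k = 2, where P = 1 − (1 − q)^6 − 6q(1 − q)^5:

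- f = 0: 1 − 0.0905 − 0.2673 = 0.642
- f = 10%: 1 − 0.1207 − 0.3060 = 0.573

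| True rate | n | Halt count | f = 0 | f = 5% | f = 10% | f = 20% |
|---|---|---|---|---|---|---|
| 33% | 6 | 2 | 0.642 | 0.609 | 0.573 | 0.499 |
| 33% | 12 | 4 | 0.597 | 0.549 | 0.498 | 0.395 |
| 33% | 18 | 6 | 0.576 | 0.516 | 0.454 | 0.332 |
| 33% | 24 | 8 | 0.562 | 0.493 | 0.423 | 0.286 |
| 40% | 6 | 2 | 0.767 | 0.734 | 0.699 | 0.622 |
| 40% | 24 | 8 | 0.808 | 0.749 | 0.680 | 0.521 |

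The f = 0 column is also the rule after the fix. Each figure is for one look and ignores repeated looks.

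**The case against.** The strongest reply is that the gap rarely opens, and most of that reply stands.

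A reader might infer that a patient with grade 3 transaminase elevation who reaches grade 4 a week later goes uncounted. On the ordinary path in Table 7.1.1 that is not so. At grade 3 or above all three agents are delayed and later restarted, and at a second occurrence only umbralisib is discontinued. A worsening during the hold comes while the patient is still on protocol therapy, and it counts. For grade 1 or 2 pneumonitis the table continues acalabrutinib. A listed event that itself leads to stopping also occurs on treatment and counts.

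A reader might also infer that the first look is badly compromised. At about one patient per month, the six patients would have roughly one to six cycles each, and few are likely to have ended all therapy. The larger missed shares at n = 6 are therefore upper-end illustrations. Nor do the documents give any figure showing that serious toxicity is concentrated after early discontinuation.

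On the reading borrowed from Section 5.9.2, an event after the last dose but before the decision to stop would count. Footnote e of the Study Calendar allows more than 30 days to pass since the last dose before the assessment is tied to the decision to end treatment. This narrows the gap further, but it does not cover events after the decision.

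The events would not go unseen. SAEs are expedited through 30 days after cessation, the PMT considers whether further enrolment is appropriate (Section 16.3), and the DSMC reviews all toxicities. That oversight is discretionary, however, and does not replace the numerical trigger.

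Finally, counting on-treatment events is a coherent choice, and the expected rate below 33% is stated under that definition without a derivation. A wider window with the same thresholds will also halt more often. Both points are fair. At a true rate of 33% the added chance of halting is the difference between table columns, for example 0.642 − 0.573 = 0.069 at n = 6 with a 10% share. What follows a halt is a temporary pause and a review.

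**Conclusion.** The point holds in a narrow form. As worded, 12.4.2 leaves out a first related listed event that arises after all agents have been permanently ended, while the patient stays in the denominator and the data are already collected. Relative to a window that includes Safety Follow-up, the omission can only lower the count.

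The size is not known. If 5% to 20% of affected patients were missed at a true rate of 33%, the single-look chance of reaching the halt count would fall from 0.64 to between 0.61 and 0.50 at 6 patients, and from 0.56 to between 0.49 and 0.29 at 24. The later reviews matter more, because more patients will have stopped by then. Yet at 24 patients little accrual remains to halt (maximum 27), so the 12- and 18-patient rows are the more practical guide. The documents do not support a claim that the rule fails at the first look or misses most toxicity in patients who stop. This is a cheap improvement to a safety trigger.

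**What to change.** In Section 12.4.2, replace the time limit in "related to protocol treatment at any time during study treatment" so that the rule counts listed related events *from the first dose through 30 days after the last dose of protocol therapy (Safety Follow-up)*. The last dose should mean that of whichever agent is stopped last. Apply the window at the first look and at every six-month review, and amend the first-look reference to available cycles so that it also takes in any safety follow-up to date. Leave the event list and both thresholds unchanged.

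The cost is a change of wording in one section. No visit, form or data item is added, because 5.7, 14.4 and Table 14.5 already provide for them. The downside is a slightly higher chance of a temporary accrual pause. If the sponsor prefers on-treatment counting, 12.4.2 should define when study treatment ends for this rule, so that all sites count alike.

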14.2.1 Ventricular arrhythmias

Ventricular arrhythmias (e.g., ventricular extrasystoles, ventricular tachycardia, ventricular arrhythmia, ventricular fibrillation, etc.) are adverse events of special interest (AESIs) for participants exposed to acalabrutinib, and must be reported to AstraZeneca expeditiously, irrespective of regulatory seriousness criteria or causality (Sections [14.5](#) and [14.7](#)).

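### Section 12.4.2 lists two toxicities at exactly grade 4 and has no entry for related deaths from unlisted causes, so some treatment-related deaths add nothing to the numeric safety count

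*Combined protocol and SAP*

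**What the plan says.** Section 12.4.2 monitors a list of adverse events that are at least possibly "related to protocol treatment at any time during study treatment". Most graded entries have no upper limit, for example "Grade ≥ 2 pneumonitis", "Grade ≥ 4 infection" and "Major hemorrhage defined as serious or Grade 3 or higher bleeding or any central nervous system bleeding". The diarrhea and liver-test entries also use a ≥ sign, and febrile neutropenia carries no grade bound.

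Two entries are written differently: "New onset grade 4 atrial fibrillation in patients without a history of atrial fibrillation" and "Severe (grade 4) cutaneous reaction". Neither has a ≥ sign. The list names neither death nor grade 5 events in general.

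The count drives the decision. At the first look, taken once the 6th patient has completed induction cycle 1, the rule is: "If more than 1 patient experience any of the toxicities above at the first monitoring, accrual will be halted". With 0 or 1 affected patients, accrual carries on and the result goes to the DSMC with the next PMT report. At the later six-monthly looks, accrual is halted temporarily if 33% or more of patients have had a listed event.

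**The concern.** The protocol grades toxicity by CTCAE v5.0, in which a fatal event is grade 5. Taken at face value, life-threatening atrial fibrillation or a life-threatening skin reaction counts toward the halt, while the same event first recorded as fatal does not. No rationale is given, and the neighbouring entries show that the authors used ≥ when they meant an open range.

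The missing death entry is the larger part of the gap. The protocol itself recognises serious risks that are not on the list. Ventricular arrhythmias are events of special interest that "must be reported to AstraZeneca expeditiously, irrespective of regulatory seriousness criteria or causality" (Section 14.2.1). Congestive cardiac failure is among the reactions seen with ublituximab plus umbralisib (Section 6.4). Tumor lysis syndrome is among the serious acalabrutinib reactions (Table 6.2.2). Section 6.2 also classes every fatal acalabrutinib reaction as unexpected, and a list of anticipated toxicities is weakest for unexpected events.

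At stake is whether the pre-specified safety boundary registers these deaths, or whether a pause in accrual after them rests on judgement alone.

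**Working it through.** **Nothing to reproduce.** The documents give no operating characteristics for the toxicity rule. The check is to read the grade bound of each entry, look for any other death-based halt, and count scenarios against the thresholds.

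**Step 1. Grade bounds (Section 12.4.2).**

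| Entry | Bound as written | Does the fatal form count? |
|---|---|---|
| Diarrhea not resolving within 3 days | ≥3 | Yes |
| Febrile neutropenia | none stated | Yes |
| Pneumonitis | ≥2 | Yes |
| AST/ALT; bilirubin | ≥4; ≥3 | Yes |
| Infection | ≥4 | Yes |
| New-onset atrial fibrillation | 4 | Not if read literally |
| Major hemorrhage | serious, or 3 and above, or any CNS bleed | Yes |
| Cutaneous reaction | 4 | Not if read literally |
| Other related death | no entry | No |

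**Step 2. Any other death-based halt?** None was found. Section 16.3 makes the PMT responsible for carrying out the stopping rules but adds no trigger. Table 14.5 governs reporting only. The six-monthly DSMC review of toxicities has no numeric threshold.

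**Step 3. Thresholds.** More than 1 of 6 means 2/6 = 33.3%, which agrees with the later 33% rule. The smallest counts that trigger a halt are:
- 12 patients: 0.33 × 12 = 3.96, so 4
- 24 patients: 0.33 × 24 = 7.92, so 8
- 27 patients (maximum accrual, Section 12.3): 0.33 × 27 = 8.91, so 9

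**Step 4. Scenarios.** In each, the unlisted related death occurs in a patient with no listed event.

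| Scenario | As written | If related deaths counted |
|---|---|---|
| First 6: two unlisted related deaths | 0/6, continue | 2/6, halt |
| First 6: one listed event, one unlisted related death | 1/6, continue | 2/6, halt |
| First 6: one unlisted related death only | 0/6, continue | 1/6, continue |
| 24 patients: seven listed, one unlisted related death | 7/24 = 29.2%, continue | 8/24 = 33.3%, halt |

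**Step 5. Halt probability at the first look.** With a per-patient counted-event probability p,

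P(halt) = 1 − (1 − p)^6 − 6p(1 − p)^5.

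For p = 0.10: 1 − 0.5314 − 0.3543 = 0.114. The rates below are assumptions, because the documents give none. Patients with an unlisted related death are taken as distinct from those with a listed event, so the two rates add.

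| Listed-event rate | As written | +2% unlisted related death | +5% | +10% |
|---|---|---|---|---|
| 10% | 0.114 | 0.156 | 0.224 | 0.345 |
| 20% | 0.345 | 0.394 | 0.466 | 0.580 |
| 30% | 0.580 | 0.622 | 0.681 | 0.767 |

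**The case against.** **Deaths are not ignored.** A reader might infer that treatment-related deaths could accumulate without any response. The documents do not support that. Table 14.5 requires expedited reporting of every SAE up to 30 days after treatment, whatever its attribution. Non-COH sites report within 24 hours (Section 14.5.2.1). An unexpected fatal event associated with the drug goes to the FDA within 7 calendar days (Section 14.6). The PMT considers whether enrolment should go on (Section 16.3), and the DSMC may act independently. At about 1 patient per month (Section 12.3), only about six patients would enrol between scheduled reviews. All of this stands, but none of it adds an unlisted death to the count.

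**12.4.2 is not the only numeric rule that stops accrual.** The Simon stage 1 rule (2 or fewer CRs in 9) also does so, and Section 12.2 scores a patient who leaves induction for toxicity before a response assessment as non-CR. That is correct. However, it is an efficacy rule and no substitute for a safety trigger, so the accurate description of 12.4.2 is the only numeric safety rule.

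**The gap is narrow.** The open-ended entries already capture the fatal forms of their events, and anyone who had a listed event before dying is counted. A patient who passes through grade 4 atrial fibrillation or a grade 4 skin reaction counts too, so only an event first recorded as grade 5 escapes. Colitis would be a weak example, since persistent grade 3 or worse diarrhea often captures it. The single-grade wording may simply be loose drafting. These limits stand and reduce the size of the point, but they leave other unlisted causes uncovered.

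**The fix is partial.** With thresholds unchanged, a death weighs the same as one febrile neutropenia. One related death in six would still give 1/6, and seven in 24 would give 29.2%, both below the boundary. That is true. The change makes the count complete and does not create a separate mortality rule.

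**It is partly a design preference.** The list is a chosen set of toxicities tied to an expected rate below 33%, and no passage contradicts it. That is fair for the death entry. It is less so for the two single-grade entries, which are out of step with their neighbours.

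**Conclusion.** The point holds as a gap in the pre-specified count. As written, a fatal atrial fibrillation or skin event first recorded at grade 5, or a related death from an unlisted cause, contributes zero to the 2-of-6 and 33% triggers. One uncounted patient is enough to change the decision (1/6 against 2/6; 7/24 against 8/24).

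Under the assumed rates, counting such deaths raises the first-look halt probability by about 4 percentage points in the mildest low-rate case (0.114 to 0.156, at 10% listed events and 2% unlisted related deaths). The rise is about 23 points at 10% and 10% (0.114 to 0.345). The documents give no basis for choosing among these rates.

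The conclusion rests on the literal reading of the two grade 4 entries and on the absence of any other death-based trigger. It does not extend to saying that safety oversight fails, or that most fatal toxicities are missed. This is a modest correction that should be made, not a flaw that undermines the trial.

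**What to change.** In Section 12.4.2:
- Write the atrial fibrillation and cutaneous entries as Grade ≥4.
- Add one entry: any Grade 5 event whose attribution to protocol therapy is possible, probable or definite under Section 14.1.
- Leave the 2-of-6 and 33% thresholds as they are.

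The cost is two symbols and one line. Grade and attribution are already assessed (Section 14.1), and all grade 3 and higher events and SAEs are already recorded (Section 14.4), so no new data are needed. The downside is a slightly higher chance of a temporary accrual pause with DSMC review. The sponsor should recognise that a single related death would then add to the count but would not by itself halt accrual at the first look.

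### The first toxicity halt in Section 12.4.2 is read only when the 6th patient completes Cycle 1, so the written rule does not itself stop accrual if a second of the first six patients qualifies earlier

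*Combined protocol and SAP*

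**What the plan says.** Section 12.4.2 (Toxicity Monitoring) lists the adverse events that count, provided they are at least possibly related to treatment, at any time during study treatment. The reference level is given as "The expected rate of patients having any of these toxicities should be <33"%.

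- **Timing and data of the first look:** "The first monitoring will occur when the 6th patient completes the first induction cycle, and it will include all available cycles from the first 6" to be treated.
- **Halt:** "If more than 1 patient experience any of the toxicities above at the first monitoring, accrual will be halted". The study committee and the data and safety monitoring committee (DSMC) then review, and accrual resumes only with DSMC approval.
- **Continue:** "If 0 or 1 patient has these toxicities at the first monitoring, accrual will continue as planned".
- **Later looks:** "Subsequent monitoring will be performed every 6 months as part of each PMT report", with a temporary halt if 33% or more of patients are affected.

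Section 12.3 projects accrual "with an estimated accrual rate of approximately 1 patient per month", and Section 5.2 sets induction cycles at 28 days. No staggered entry, pause between patients or earlier numerical trigger is stated.

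**The concern.** The rule counts affected patients among the first six, over all their available cycles. Barring re-attribution, that count only rises. Once a second of the six is affected, the outcome of the first look is very likely settled, yet the instruction to halt waits until the sixth patient has been enrolled and has finished a cycle. Patients entering in between are treated after the protocol's own criterion for DSMC review has in substance been met.

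This matters more here than in a trial of a familiar regimen. The cited triplet experience used ibrutinib, in relapsed disease (Section 2.1.5). The evidence cited for acalabrutinib with a PI3K inhibitor is a mouse model using a different PI3K inhibitor (Section 2.1.4). Section 2.3 says that previously untreated patients are at greater risk of immune-mediated toxicity from this drug class. The documents cite no clinical data on the acalabrutinib triplet itself, so the six-patient rule serves as the run-in safeguard.

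**Working it through.** The plan gives no operating characteristics for the toxicity rule, so there is no stated figure to reproduce. The check therefore starts from the rule.

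**Inputs from the documents:** a boundary of 2 or more of 6 patients, read when patient 6 completes Cycle 1 (12.4.2); a reference rate of 33% (12.4.2); about one patient per month (12.3); 28-day cycles (5.2).

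**Assumptions:** true toxicity rates p of 20% and 50% as a range around 33%; patients independent; each patient's outcome known before the next patient starts.

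**Calendar.** With 30.4 days between entries, patient 6 starts on day 5 × 30.4 = 152 and completes Cycle 1 on day 180, about month 6. A 6-monthly review need not fall any earlier.

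**Crossing the boundary.** The second affected patient is the k-th enrolled with probability

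P(k) = (k − 1) p² (1 − p)^(k − 2), k = 2, …, 6,

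and 6 − k of the first six then start after crossing. At p = 0.33:

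| k | P(k) | further patients, 6 − k |
|---|---|---|
| 2 | 0.1089 | 4 |
| 3 | 0.1459 | 3 |
| 4 | 0.1467 | 2 |
| 5 | 0.1310 | 1 |
| 6 | 0.1097 | 0 |

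- P(halt) = sum of the column = 0.642, which equals the binomial P(X ≥ 2 of 6).
- Crossed by patient 4: 0.1089 + 0.1459 + 0.1467 = 0.401 (unrounded terms).
- At least one further patient: 0.642 − 0.110 = 0.532.
- Mean over all trials: 4(0.1089) + 3(0.1459) + 2(0.1467) + 0.1310 = 1.30.
- Mean given a halt: 1.298 / 0.642 = 2.02.

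**Range over the assumed rates:**

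| True rate | P(halt) | At least 1 further | 4 further | Mean, all trials | Mean given halt |
|---|---|---|---|---|---|
| 20% | 34.5% | 26.3% | 4.0% | 0.59 | 1.70 |
| 33% | 64.2% | 53.2% | 10.9% | 1.30 | 2.02 |
| 50% | 89.1% | 81.3% | 25.0% | 2.25 | 2.53 |

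**Timing, by simulation.** With fixed monthly entry and onset uniform over Cycle 1, the mean delay from crossing to the look is about 66, 75 and 91 days at the three rates, and never more than 4 further patients start.

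**Sensitivity to the assumptions:**
- *Later onset.* With fixed monthly entry and a 33% rate, spreading onset over three cycles lowers the mean given a halt to about 1.6, and over six cycles to about 1.1.
- *Irregular accrual.* With Poisson entry at the same average rate and Cycle 1 onset, patients beyond the sixth can start while patient 6 completes the cycle. The mean total given a halt becomes about 2.1, 2.5 and 3.0 at the three rates, and individual trials can exceed 4.

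**With the change under Fix.** The chance of crossing by the first look is the same (64.2% at 33%). Patients started after crossing fall to 0 under the same assumption.

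**The case against.** **Other oversight exists.** Section 16.3 makes the Protocol Management Team (PMT) responsible for ongoing safety monitoring, including carrying out the stopping rules, and its meetings consider whether further enrolment is appropriate. Registration is central, with slots verified by the coordinating center (4.2). Serious events are expedited (14.5), within 24 hours from outside sites, and adverse event forms are due within 10 days (13.3). Nothing in 12.4.2 forbids an earlier pause. A reader might infer that the plan requires enrolment to go on regardless; the documents do not support that. What remains is that all these provisions are discretionary. The PMT is only recommended to meet, with no interval stated, and the rule it carries out is the one in 12.4.2. Some listed toxicities, such as Grade 2 pneumonitis, need not be serious and may arrive only on routine forms.

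**The halt is not strictly certain after a second event.** Qualification depends on attribution, which is the site investigator's judgment (14.1), and Section 7.1 allows for an event later found unrelated. This stands: very likely is the right word.

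**The first look may be past.** Section 7.1 says reversible liver toxicity has been seen on study, and Section 6.1 mentions an amendment. The documents do not say how many patients have been treated, so it is unknown whether a rule for the first six can still act.

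**A fixed look at six patients is a recognisable design choice.** Agreed. The documents neither contradict themselves nor give a wrong figure here. The point is a cheap improvement.

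**Conclusion.** The point holds as a gap in when the rule acts. Section 12.4.2 ties the first halt to one look, and no other section obliges a pause when a second of the first six patients qualifies sooner. At a 33% toxicity rate, further patients start after crossing in about 53% of trials, with a mean of 2.0 given a halt and 1.3 over all trials. These figures rest on independent outcomes, each known before the next patient starts. Only the 33% is the protocol's; the other rates are assumptions.

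Three stronger readings should be resisted:
- A reader might take four extra patients as the expected exposure. It is the extreme among the first six, with probability 10.9% at 33% and 4.0% at 20%.
- A reader might add a further patient entering during patient 6's Cycle 1. At exactly monthly spacing the 28-day cycle ends before patient 7 starts; the addition arises only with irregular accrual.
- A reader might count any two events. The rule counts patients, so two events in one patient do not cross the boundary.

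**What to change.** Keep the threshold, event list and DSMC process, and state in Section 12.4.2:

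*If, before the first monitoring, a second of the first 6 treated patients has a qualifying toxicity, accrual will be halted at that time and reviewed as described; otherwise the first monitoring is performed when the 6th patient completes Cycle 1.*

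The limit to the period before the first monitoring is essential. Events count throughout treatment, so an open-ended trigger would also fire if one of the first six had an event by the first look and a second had one in Cycle 5, with 12 patients treated. The present rule would see 2/12 = 17% and not halt.

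The cost is one sentence. Central registration makes an immediate halt practicable. The chance of crossing the boundary by the first look does not change; the downside is an occasional halt on an event later re-attributed as unrelated. If six patients have already completed Cycle 1, the sentence has no effect.

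Checking the 33% rule at each new event, as well as every 6 months, is a separate and optional change. It adds looks and temporary halts, and should be adopted only after its operating characteristics are computed.
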